### 9.5.3 Appropriateness of Measurements

All clinical assessments are standard measurements commonly used in studies of initial adjunctive treatment for POS with or without SGS.

The safety assessments to be performed in this study, including assessment of AEs and SAEs, discontinuation from treatment, prior and concomitant medication usage, periodic measurement of weight, and assessments of cognitive functioning and monitoring of suicidal thoughts or depressive symptoms, are standard evaluations to ensure subject safety.

### 9.5.4 Reporting of Serious Adverse Events, Pregnancy, and Events Associated With Special Situations

#### 9.5.4.1 Reporting of Serious Adverse Events

**All SERIOUS ADVERSE EVENTS, regardless of their relationship to study treatment, must be reported on a completed SAE form by email or fax as soon as possible but (in US) no later than 1 business day or (in EU) no later than 24 hours from the time at which the investigator becomes aware of the event.**

SAEs, regardless of causality assessment, must be collected through the last visit. All SAEs must be followed to resolution or, if resolution is unlikely, to stabilization. Any SAE judged by the investigator to be related to the study treatment or any protocol-required procedure should be reported to the sponsor regardless of the length of time that has passed since study completion.

The detailed contact information for reporting of SAEs is provided in the ISF.

For urgent safety issues call: Designated CRO (C&R Research) contact number.

**For urgent safety issues**, please ensure all appropriate medical care is administered to the subject and contact the appropriate study team member listed in the ISF.

It is very important that the SAE report form be filled out as completely as possible at the time of the initial report. This includes the investigator's assessment of causality.

Any follow-up information received on SAEs should be forwarded within 1 business day of its receipt. If the follow-up information changes the investigator's assessment of causality, this should also be noted on the follow-up SAE form.

Preliminary SAE reports should be followed as soon as possible by detailed descriptions including copies of hospital case reports, autopsy reports, and other documents requested by the sponsor.

The investigator must notify his/her IRB/IEC of the occurrence of the SAE in writing, if required by their institution. A copy of this communication must be forwarded to the sponsor to be filed in the sponsor's Trial Master File.

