**9.1.4 Follow-Up Period (4 weeks)**

The Follow-Up Period will begin at the end of the Maintenance Period. Subjects may continue to receive commercial perampanel during the Follow-Up Period. (revised per Amendment 01) At the end of the Follow-Up Period, a Follow-Up Visit will take place. Subjects who are withdrawn from the study for any reason will also undergo a Follow-Up Visit.

The end of the study will be the date of the last study visit for the last subject. However, if there are AEs that are present and not resolved at the last scheduled visit, these AEs should be followed to stabilization or resolution.

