##### **9.5.1.6.1 ADVERSE EVENTS AND EVENTS ASSOCIATED WITH SPECIAL SITUATIONS**

An AE is any untoward medical occurrence in a subject or clinical investigation subject administered an investigational product. An AE does not necessarily have a causal relationship with the medicinal product. For this study, the study drug is perampanel.

The criteria for identifying AEs in this study are:

- Any unfavorable and unintended sign (including an abnormal laboratory finding), symptom, or disease temporally associated with the use of an investigational product, whether or not considered related to the investigational product (Note: A sign or symptom should not be listed as a separate AE if the applicable disease [diagnosis] is being reported as an AE)
- Any new disease or exacerbation of an existing disease
- Any deterioration in nonprotocol-required measurements of a laboratory value or other clinical test (eg, electrocardiography or x-ray) that results in symptoms, a change in treatment, or discontinuation of study drug
- Recurrence of an intermittent medical condition (eg, headache) not present at pretreatment (ie, at baseline)

An abnormal laboratory test result should be considered an AE if the identified laboratory abnormality leads to any type of intervention, withdrawal of study drug, or withholding of study drug, whether prescribed in the protocol or not.

All AEs observed during the study will be reported on the eCRF. All AEs, regardless of relationship to study drug or procedure, should be recorded beginning from the time the subject signs the study ICF through the last visit. Subjects who fail screening primarily due to AE(s) must have the AE(s) leading to screen failure reported on the Screening Disposition eCRF. SAEs will be collected for 28 days after the last dose.

Abnormal laboratory values should not be listed as separate AEs if they are considered to be part of the clinical syndrome that is being reported as an AE. It is the responsibility of the investigator to review all laboratory findings in all subjects and determine if they constitute an AE. Medical and scientific judgment should be exercised in deciding whether an isolated laboratory abnormality should be classified as an AE. Any laboratory abnormality considered to constitute an AE should be reported on the Adverse Event eCRF.

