It is the responsibility of the investigator to review the results of the C-SSRS in all subjects and determine if any result constitutes an AE. Medical and scientific judgment should be exercised in deciding whether an isolated suicidality rating scale response should be classified as an AE.

All AEs must be followed for 28 days after the subject's last dose, or until resolution, whichever comes first.

Every effort must be made by the investigator to categorize each AE according to its severity and its relationship to the study treatment.

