### 8.2.2 Treatment Duration for Safety Analyses

For AEs, the treatment duration is considered to begin on Day 1 and ends 28 days after the last dose of treatment.

For summaries of safety by time points, the time points will be relative to date of first dose. For standardized reporting, study day windows relative to the first dose (Day 1) in the study will be applied to determine into which study week the data will be mapped. Scheduled, unscheduled, and early withdrawal visits will be mapped into study weeks. Table 1 below gives the mapping of relative day ranges to week for non-AE safety variables. If a subject did not have a recorded observation falling within a given range of days in order to be assigned to a study week, the subject's data for that week will be regarded as missing for summarization purposes. If there are two or more assessments in the same window then:

- if the window is the baseline assessment, then the latest assessment will be used in the summary tables.
- if the window is not the baseline assessment, then the assessment closest to the scheduled assessment will be used in the summary tables.

Note that if two assessments are equidistant from the scheduled assessment then the last assessment of the two (within the allowable window) will be used.

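### The protocol gives conflicting end points for SAE collection and for AE follow-up, and it records AEs only to the last visit, which can fall a few days short of the SAP's 28-day window

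*Protocol*

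**What the plan says.** **SAE collection.** Protocol 9.5.1.6.1: "SAEs will be collected for 28 days after the last dose". Protocol 9.5.4.1: "SAEs, regardless of causality assessment, must be collected through the last visit". Section 9.5.4.1 adds that SAEs judged related to treatment or to a protocol-required procedure remain reportable with no time limit.

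**Recording of AEs.** Under Protocol 9.5.1.6.1, all AEs "should be recorded beginning from the time the subject signs the study ICF through the last visit".

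**Follow-up of AEs.** Protocol 9.5.1.6.1: "All AEs must be followed for 28 days after the subject's last dose, or until resolution, whichever comes first". Protocol 9.1.4: "if there are AEs that are present and not resolved at the last scheduled visit, these AEs should be followed to stabilization or resolution". Protocol 9.3.3.1 makes completion of the study depend on resolution of any AE present at the last visit. For SAEs, 9.5.1.6.2 and 9.5.4.1 agree on follow-up to resolution or, failing that, stabilization.

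**Analysis window.** SAP 8.2.2: "For AEs, the treatment duration is considered to begin on Day 1 and ends 28 days after the last dose of treatment".

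**Timing of the last visits.** Protocol Table 4 puts Visit 7 at Week 52 (Day 365) and Visit 8 at Week 56. Footnote b gives a ±7-day window to visits in the Titration, Maintenance and Follow-Up columns. Section 9.1.4 starts the 4-week Follow-Up Period at the end of the Maintenance Period and puts the Follow-Up Visit at its end.

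**The concern.** There are three inconsistencies.

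- SAE collection has two end points, and no section says which governs when they differ.
- For an AE still unresolved 28 days after the last dose, one section lets follow-up stop and two others do not.
- The SAP counts treatment-emergent AEs over a period defined by the last dose, while the protocol records them over a period defined by the last visit. No section requires the last visit to be at least 28 days after the last dose.

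At stake are complete capture of late events in the SAP's safety tables, uniform practice across up to approximately 25 sites, and proper follow-up of patients with unresolved events.

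**Working it through.** The documents give no figure for this gap, so there is none to reproduce. The check is day arithmetic.

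**Inputs**
- Table 4 study days follow 7 × week + 1: Weeks 2, 4, 13, 26, 39 and 52 give Days 15, 29, 92, 183, 274 and 365, all as printed.
- Visit 8 has no printed study day. The same rule gives 7 × 56 + 1 = Day 393.
- Last dose: assumed to be the night before Visit 7. Dosing is at bedtime (Protocol 9.4.1), and Table 4 shows study drug returned but not dispensed at Visit 7.
- The SAP takes the last dose from the study-drug end date on the CRF (SAP 8.1.2), so commercial perampanel during follow-up is assumed not to move it.
- Let w be the deviation of Visit 7 and u the deviation of Visit 8, each from -7 to +7 days.

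**Nominal schedule.** Last dose Day 364, Visit 8 Day 393: 393 - 364 = 29 days. No shortfall.

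**Reading A: Visit 8 timed 4 weeks ±7 days from the actual Visit 7**
- Gap = 28 + u + 1 = 29 + u; minimum 29 - 7 = 22 days.
- Maximum shortfall = 28 - 22 = 6 days.
- Short for u = -7 to -2: 6 of 15 positions (40%).
- Mean over all positions = (6+5+4+3+2+1)/15 = 21/15 = 1.4 days.

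**Reading B: both windows float independently around the fixed schedule**
- Gap = (393 + u) - (365 + w - 1) = 29 + u - w.
- Minimum (w = +7, u = -7) = 15 days: last dose Day 371, Visit 8 Day 386. The SAP window runs to 371 + 28 = Day 399, so Days 387 to 399 are uncovered: 13 days.
- Maximum (w = -7, u = +7) = 43 days, which is 15 days beyond the window.
- Short when w - u is at least 2: 13 + 12 + ... + 1 = 91 of 225 combinations (40.4%).
- Mean over all combinations: the sum of k(14 - k) for k = 1 to 13 is 455; 455/225 = 2.0 days.

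**Scale.** On the nominal schedule the SAP's AE window is 364 + 28 = 392 days. The mean shortfall is 1.4/392 = 0.4% of it under A and 2.0/392 = 0.5% under B.

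**Sensitivity.** If a dose is counted on the day of Visit 7, the maxima become 7 days (A) and 14 days (B). The nominal gap is then exactly 28 days, still with no shortfall.

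**Which events are exposed**

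| Event | Collection end point | Exposed to the shortfall? |
|---|---|---|
| Non-serious AE | Last visit (9.5.1.6.1) | Yes, on a plain reading |
| SAE judged unrelated | 28 days (9.5.1.6.1) or last visit (9.5.4.1) | Only if a site follows 9.5.4.1 instead of 9.5.1.6.1 |
| SAE judged related | No time limit (9.5.4.1) | No |

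**The case against.** The strongest reply is that the two SAE rules can both be obeyed. Neither says that collection stops at its end point, so a site that collects to the later of the two dates loses nothing against the SAP window. Section 9.5.4.2 writes out that combination for pregnancy reports. This stands, and it limits the SAE gap to sites that follow 9.5.4.1 instead of 9.5.1.6.1, and there to SAEs judged unrelated. It does not remove the ambiguity, because the SAE sections lack the combined wording. Nor does it help non-serious AEs, whose recording ends at the last visit.

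The second reply is that the shortfall is small, absent on the nominal schedule, and arises in a descriptive study with no control arm, so no between-arm comparison is affected. That also stands.

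Some stronger readings are tempting, but the documents do not support them:
- *Thirteen days as a flat figure.* It needs a late Visit 7, an early Visit 8 and independently floating windows. Section 9.1.4 can equally be read as timing Visit 8 from the actual end of maintenance, which gives 6 days.
- *Forty percent of completers affected.* This assumes visits spread evenly over their windows, which no section supports, and it counts shortfalls of a single day.
- *Follow-up length distorts incidence.* The SAP counts a subject once per SOC and preferred term (5.6.2, 8.2.3). How long a recorded AE is followed does not change that count; at most it could change the recorded maximum severity.
- *Withdrawn subjects lose nearly the whole 28 days.* That could follow for subjects withdrawn after Week 39 if Table 4 footnote c limits the Follow-Up Visit to those withdrawn before Visit 6. But 9.1.4 gives every withdrawn subject a Follow-Up Visit, so the text does not establish that loss.

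**Conclusion.** The concern holds as an internal inconsistency: wrong as written, minor in severity. The current text gives two end points for SAE collection, two incompatible rules for follow-up of unresolved AEs, and a recording period for AEs that need not cover the SAP's analysis window.

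For completers the uncovered part of the window is zero on the nominal schedule and at most 6 or 13 days, depending on how Visit 8 is timed. The averages of 1.4 and 2.0 days rest on evenly spread visits, and all these figures assume a last dose on the night before Visit 7. The consequence is a small understatement of treatment-emergent AE incidence, mainly for non-serious events. The follow-up conflict is a matter of consistency between sites and of patient safety, not of incidence. It would go too far to infer that SAEs are generally lost or that the safety tables are materially wrong.

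**What to change.** Reconcile Protocol 9.5.1.6.1, 9.5.4.1, 9.1.4 and 9.3.3.1 to one collection period and one follow-up rule. Which rules to adopt is for the sponsor. From the analysis side there is one requirement: recording of AEs and SAEs should cover at least the whole SAP 8.2.2 window. The two periods need not be equally long, because the SAP cuts off at 28 days and longer collection does no harm. Otherwise, SAP 8.2.2 should be shortened to the period actually observed. When 9.1.4 is revised, Table 4 footnote c should be reconciled with it.

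The cost is a protocol clarification and possibly a telephone contact for subjects whose Visit 8 is early. SAP section 7 reports that enrollment has been terminated. If follow-up visits are already complete, the remaining step is to state in the SAP or the study report how many subjects had their last visit fewer than 28 days after the last dose, and by how many days.

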#### 9.5.4.2 Reporting of Pregnancy and Exposure to Study Drug Through Breastfeeding

Any pregnancy in a female subject in which the estimated date of conception is either before the last visit or within 28 days of last study treatment, or any exposure to study drug through breastfeeding during study treatment or within 28 days of last study treatment, must be reported.

If an adverse outcome of a pregnancy is suspected to be related to study drug exposure, this should be reported regardless of the length of time that has passed since the exposure to study treatment.

A congenital anomaly, death during perinatal period, an induced abortion, or a spontaneous abortion are considered to be an SAE and should be reported in the same time frame and in the same format as all other SAEs (see Reporting of Serious Adverse Events [Section 9.5.4.1]).

Pregnancies or exposure to study drug through breastfeeding must be reported by fax or email as soon as possible but no later than 1 business day from the date the investigator becomes aware of the pregnancy. The contact information for the reporting of pregnancies and exposure to study drug through breastfeeding is provided in the ISF. The Pregnancy Report Form must be used for reporting. All pregnancies must be followed to outcome. The outcome of the pregnancy must be reported as soon as possible but no later than 1 business day from the date the investigator becomes aware of the outcome.

A subject who becomes pregnant must be withdrawn from the study.

#### 9.5.4.3 Reporting of Events Associated With Special Situations

##### **9.5.4.3.1 REPORTING OF ADVERSE EVENTS ASSOCIATED WITH STUDY DRUG OVERDOSE, MISUSE, ABUSE, OR MEDICATION ERROR**

AEs associated with study drug overdose, misuse, abuse, and medication error refer to AEs associated with uses of the study drug outside of that specified by the protocol. Overdose, misuse, abuse, and medication error are defined as follows:

**Overdose:** Accidental or intentional use of the study drug in an amount higher than the protocol-defined dose.

**Misuse:** Intentional and inappropriate use of study drug not in accordance with the protocol.

**Abuse:** Sporadic or persistent intentional excessive use of study drug accompanied by harmful physical or psychological effects.

**Medication error:** Any unintentional event that causes or leads to inappropriate study drug use or subject harm while the study drug is in the control of site personnel or the subject.

All AEs associated with overdose, misuse, abuse, or medication error should be captured on the Adverse Event eCRF and also reported using the procedures detailed in Reporting of

Serious Adverse Events ([Section 9.5.4.1](#)) even if the AEs do not meet serious criteria. Abuse is always to be captured as an AE. If the AE associated with an overdose, misuse, abuse, or medication error does not meet serious criteria, it must still be reported using the SAE form and in an expedited manner but should be noted as nonserious on the SAE form and the Adverse Event eCRF.

#### 9.5.4.4 Expedited Reporting

The sponsor must inform investigators and regulatory authorities of reportable events, in compliance with applicable regulatory requirements, on an expedited basis (ie, within specific time frames). For this reason, it is imperative that sites provide complete SAE information in the manner described above.

#### 9.5.4.5 Breaking the Blind

Not applicable.

#### 9.5.4.6 Regulatory Reporting of Adverse Events

AEs will be reported by the sponsor or a third party acting on behalf of the sponsor to regulatory authorities in compliance with local and regional law and established guidance. The format of these reports will be dictated by the local and regional requirements.

All studies that are conducted within any European country will comply with European Good Clinical Practice Directive 2005/28/EC and Clinical Trial Directive 2001/20/EC. All suspected unexpected serious adverse reactions will be reported, as required, to the competent authorities of all involved European member states.

### 9.5.5 Completion/Discontinuation of Subjects

A subject may elect to discontinue the study at any time for any reason. All subjects who discontinue the study are to complete the study's early discontinuation procedures indicated in the Schedule of Procedures/Assessments ([Table 4](#)).

The investigator will promptly explain to the subject involved that the study will be discontinued for that subject and provide appropriate medical treatment and other necessary measures for the subject. A subject who has ceased to return for visits will be followed up by mail, phone, or other means to gather information such as the reason for failure to return, the status of treatment compliance, the presence or absence of AEs, and clinical courses of signs and symptoms.

Subjects who discontinue early from the study will be discontinued for 1 of these primary reasons: AE(s), lost to follow-up, subject choice, inadequate therapeutic effect, progression of disease, withdrawal of consent, pregnancy, study terminated by sponsor, or other. In addition to the primary reason, the subject may indicate 1 or more secondary reason(s) for discontinuation. Study disposition information will be collected on the Subject Disposition eCRF.

A subject removed from the study for any reason may not be replaced.

#### 9.5.6 Abuse or Diversion of Study Drug

During the study, the investigator will report any concern about abuse or diversion of study drug. AEs associated with abuse or diversion will be appropriately reported as AEs and monitored per [Section 9.5.4](#). Abuse is always to be captured as an AE.

### 9.6 Data Quality Assurance

This study will be organized, performed, and reported in compliance with the protocol, standard operating procedures, working practice documents, and applicable regulations and guidelines. Site audits will be made periodically by the sponsor's or the CRO's qualified compliance auditing team, which is an independent function from the study team responsible for conduct of the study.

#### 9.6.1 Data Collection

Data required by the protocol will be collected on the eCRFs and entered into a validated data management system that is compliant with all regulatory requirements. As defined by ICH guidelines, the eCRF is a printed, optical, or electronic document designed to record all of the protocol-required information to be reported to the sponsor on each study subject.

Data collection on the eCRF must follow the instructions described in the eCRF Completion Guidelines. The investigator has ultimate responsibility for the collection and reporting of all clinical data entered on the eCRF. The investigator or designee must sign the completed eCRF to attest to its accuracy, authenticity, and completeness.

Completed, original eCRFs are the sole property of Eisai and should not be made available in any form to third parties without written permission from Eisai, except for authorized representatives of Eisai or appropriate regulatory authorities.

#### 9.6.2 Clinical Data Management

All software applications used in the collection of data will be properly validated following standard computer system validation that is compliant with all regulatory requirements. All data, both eCRF and external data, will be entered into a clinical system.

### 9.7 Statistical Methods

All statistical analyses will be performed by the sponsor or designee after the study is completed and the database is locked and released. Statistical analyses will be performed using SAS software or other validated statistical software as required. Details of the statistical analyses will be included in a separate statistical analysis plan, which will be finalized before database lock.

## 9.7.1 Statistical and Analytical Plans

All summaries of seizure-related efficacy endpoints will be produced by seizure type (POS, SGS, and PGTCS). Summaries of retention rate and safety data will be produced by seizure type (POS and PGTCS) and overall.

### 9.7.1.1 Study Endpoints

#### 9.7.1.1.1 PRIMARY ENDPOINT

The primary endpoint is retention rate, defined as the proportion of subjects remaining on perampanel at the specified time points: 3, 6, 9, and 12 months after initiation of treatment.

